7.4.2 Permitted

- Immunosuppressants
- Vitamin B12 and folic acid supplements/replacement are allowed during the study.
- Over the Counter (OTC) oral supplements/multivitamin type preparations (including those that contain iron) may be taken, however subjects should keep the same dose during the study.
- Oral contraceptives are allowed during the study.

CONFIDENTIAL Page 46 of 80

 All other concomitant medications must remain stable from Screening and throughout the study.

7.4.3 Potential Medication Interactions

Iron-drug interactions of clinical significance have been reported to occur with a large number of concomitant therapies. Concurrent ingestion of oral iron causes marked decrease in the bioavailability of a number of drugs due to the formation of iron-drug complexes (chelation or binding of iron by the second drug). Examples of affected drugs are: penicillamine, bisphosphonates, ciprofloxacin, entacapone, levodopa, levofloxacin, levothyroxine (thyroxine) moxifloxacin, mycophenolate, norfloxacin, ofloxacin, tetracyclines, calcium and magnesium salts, dimercaprol, chloramphenicol and methyldopa.

Based on the recent Phase I study finding, ferric maltol oral suspension can be taken at least 30 mins after a meal. To minimise the potential for drug interactions, patients should wait at least 4 hours before taking other concomitant medications and/or supplements. The exact timing of any concomitant medication and its iron content should be recorded in the eCRF.

7.5 INDIVIDUAL DISCONTINUATION CRITERIA

Subjects and/or their parents or guardians have the right to withdraw consent without prejudice at any time during the study. If a subject withdraws consent, the Investigator should make a reasonable effort to determine the cause. All withdrawn subjects should have a Post-Treatment Safety Visit within 10-14 days after the last dose of study drug (if the subject agrees in the case of withdrawn consent).

If there is any sign of accumulation of maltol or glucuronide in the pre-assignment phase PK day for subject population aged 1 month to less than 2 years, the recruitment to this age group will be suspended and they will not enter the treatment phase until the risk has been assessed and approved via a substantial amendment to the protocol.

Subjects may be discontinued prematurely during the study for the following reasons:

- Withdrawal of informed consent
- A drop of >1 g/dl in Hb from baseline
- Unwillingness or inability to comply with protocol requirements
- Pregnancy or not using a reliable method of birth control (female subject of childbearing potential)
- Use of prohibited concomitant medications
- Serious adverse events that are judged by the Investigator to be related to study treatment

CONFIDENTIAL Page 47 of 80

- Blood transfusions for any cause during the study treatment period
- Use of any other single agent prescribed iron medications
- Occurrence of any condition that, in the opinion of the Investigator, significantly
 jeopardizes the wellbeing and safety of the patient, including any intolerable toxicity
 related to study treatment determined by the investigator to be unacceptable given
 the severity of the event

The reason for study drug discontinuation and the date of last dose should be recorded in the eCRF. Subjects who discontinue treatment prematurely must return for the Post-Treatment Safety Visit, unless informed consent is withdrawn (and the subject and/or their parents or guardians do not agree to attend this follow-up visit). A subject who meets discontinuation criteria should be discussed on an individual basis with the Medical Monitor.

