6 STUDY OBJECTIVES AND ENDPOINTS

6.1 PRIMARY OBJECTIVES:

- To compare the safety and gastrointestinal tolerability of ferric maltol oral suspension and ferrous sulfate oral liquid in children and adolescents aged 2 years to 17 years and assess the safety and tolerability of ferric maltol oral suspension in children 1 month to less than 2 years, in the treatment of iron deficiency anaemia during the 12 weeks treatment period.
- 2. To assess the effect on haemoglobin in children and adolescents aged 1 month to 17 years after twice daily ferric maltol oral suspension administration for 12 weeks

6.2 SECONDARY OBJECTIVES:

- 1. To assess the pharmacokinetics (PK) in children and adolescents aged 2 to 17 years after a single dose of ferric maltol oral suspension on Visit 2 (PK Day 1), and after twice daily administration for at least 6 days, on Visit 3 (PK Day 2), after a single morning dose, through measurement of serum iron, corrected serum iron, transferrin saturation (TSAT) and plasma maltol and maltol glucuronide
- 2. To assess the effect on iron markers in children and adolescents aged 1 month to 17 years after twice daily ferric maltol oral suspension administration for 12 weeks
- 3. To assess the PK, in children aged 1 month to less than 2 years of age after a single dose of ferric maltol oral suspension (Pre-assignment PK visit) and after twice daily administration for at least 6 days, on Visit 3 (PK Day 2), after a single morning dose, through measurement of serum iron, corrected serum iron, transferrin saturation (TSAT) (PK Day 2 only), plasma (PK Day 2 only) and urine concentration of maltol and maltol glucuronide
- 4. To assess the effect, in children aged 1 month to less than 2 years of age after twice daily administration for at least 6 days, on Visit 3 (PK Day 2) after a single morning dose, on serum transferrin, total and unsaturated iron binding capacity (TIBC, UIBC)
- 5. To assess the effect, in children aged 2 to 17 after a single dose of ferric maltol suspension Visit 2 (PK Day 1), and after twice daily administration for at least 6 days, on Visit 3 (PK Day 2) after a single morning dose, on serum transferrin, total and unsaturated iron binding capacity (TIBC, UIBC).
- 6. To compare the palatability from age-appropriate scoring system of ferric maltol oral suspension and ferrous sulfate oral liquid

CONFIDENTIAL Page 40 of 80

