Subjects aged 2-17 will be randomised 1:1 to receive ferric maltol oral suspension or ferrous sulfate oral liquid. The first 12 subjects randomised to ferric maltol in each age sub-groups (2 – 9 yrs, 10 – 17 yrs, respectively) will enter a Pharmacokinetic phase from Visit 2 (PK Day 1) till Visit 3 (PK Day 2) with 2 PK days. Following baseline pre-dose blood sample, subjects will take a single dose of 2.5 ml (2 yrs -11 yrs) or 5 ml (12 yrs - 17 yrs) ferric maltol oral suspension under supervision and then a further 2 PK blood samples will be taken up to 6 hours. Following the last scheduled PK sample on PK Day 1 (Visit 2), subjects will be reminded to take their dose twice daily until PK Day 2 (between Day 7-Day 10). On PK Day 2 (Visit 3) subjects should withhold their morning dose until attending their second PK assessment day. Same procedure will be repeated for PK assessment as on PK Day 1. Following PK Day 2, subjects will continue treatment until Week 12.

Once the 12 subjects in each age subgroup (2 - 9 yrs, 10-17 yrs, respectively) have finished their PK visits, they will continue on treatment until week 12. Further subjects will not need to have PK samples taken.

Subjects randomised to ferrous sulfate oral liquid will not need to complete the PK period, they will remain on oral ferrous sulfate until Week 12. Ferrous sulfate 125 mg/ml (25 mg/ml elemental iron) or equivalent dose will be used for all children/adolescents. To maximise the iron replenishment for subjects within this group as well; aged 2 - 17 yrs will be dosed 0.24ml (6mg elemental iron) per kg body weight, up to a maximum of 8ml given daily in two divided doses.

 Assigned treatment phase: 12 weeks open label treatment for ferric maltol children aged 1 month to less than 2 years

Once the PK samples have been analysed for subjects aged 1 month to less than 2 years and they can enrol in the randomisation phase, they will be assigned to receive ferric maltol oral suspension and start the 0.1 ml/kg/dose, BID on Visit 2 for 7-10 days. On Visit 3 (PK Day 2), following baseline pre-dose blood sample and urine sample, subjects will take a single dose of 0.1 ml/kg ferric maltol suspension under supervision and then a further three PK blood samples and urine samples will be taken at three timepoints up to 12 hours. Subjects will continue treatment until week 12.

- End of study: Week 12 visit

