9.2 RANDOMISATION (Visit 2)

Subjects will be registered into the study at the Screening visit and assigned a unique subject identification number in the IRT. Subjects will be categorised during the screening process based upon their age (2 to \leq 9 years of age and 10 to \leq 17 years of age) and their gender. Age and gender will be incorporated into the randomisation as stratification factors. A minimum of 18 subjects must be recruited into the 2-9 and 10-17 age group and a minimum of 25% of either sex must be recruited. Maximum of 12 subjects will be recruited in the 1 m - 2 yrs cohort. In the event of a subject having a birthday whilst on study and they move to a different age cohort -they will remain in the baseline cohort for the duration of the study.

A final eligibility evaluation must be conducted by the Investigator/designee prior to randomisation/pre-assignment PK visit via IRT, once the results of all Screening assessments are available.

Subjects aged 1 month to < 2 years:

Following the eligibility evaluation, a maximum of 12 subjects will enter a Pre-assignment phase: 1-day Pharmacokinetic assessment day following a single dose of 0.1 ml/kg ferric maltol oral suspension. Once the PK samples have been analysed and evidence is showing metabolism and elimination of maltol, subjects will be assigned to ferric maltol oral suspension treatment phase. Subjects will be eligible to enter the treatment phase if their maltol level returns to baseline, or to a level confirming there is no accumulation of maltol

CONFIDENTIAL Page 52 of 80

or maltol glucuronide. The sample results will be analysed on an individual basis. The Sponsor's Medical Monitor will make a recommendation to the investigator based on preassignment results. The investigator will make the final decision if subjects aged 1 month to < 2 years are eligible to enter the treatment phase.

Subjects aged 2 years to 17 years:

No subject may begin treatment prior to being randomised in the IRT. The randomisation procedure (created using a computer-generated random permutation procedure) will assign the subject to one of the treatment arms.

Initial dosing with ferric maltol and ferrous sulfate must occur on the same day of randomisation. The date of Visit 2 is the date of first dose with ferric maltol or ferrous sulfate.

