- 6. Pre-assignment phase: All subjects in 1 m-< 2 yrs age group will enter a 1-day PK assessment day prior to entering the treatment phase. Pre-assignment PK Day, each subject has baseline PK urine samples collected immediately prior to ferric maltol dosing (0 h). Following this, subjects will take a single dose of 0.1 ml/kg ferric maltol under supervision. Three (3) PK urine samples will be taken between 0.5 hr -3 hrs, 3 hrs -6 hrs, and 7 hrs -12 hrs post dose. N.B: samples should be taken at least 1.0 h apart. Urine collections instructions are detailed in the study's Laboratory Manual.

PK Day 2 (Visit 3), each subject has baseline PK blood and urine samples collected immediately prior to ferric maltol dosing (0 h). Following this, subjects will take a single dose of 0.1 ml/kg ferric maltol under supervision. Three PK Post-dose blood samples will be collected at the following windows 1.0-2.0 hrs, 3.0-4.0 hrs and 10.0-12.0 hrs; post-dose urine samples will be taken between 0.5 hr -3 hrs, 3 hrs -6 hrs and 7 hrs -12hrs post dose.

In the event of an administered dose not being consumed or partially consumed by the patient this will be noted as a missed dose and will not be repeated.

- 7. Eligibility laboratory sampling/assessments must be completed before the subject is assigned to ferric maltol. The PK samples will be analysed and if evidence of metabolism and elimination of maltol is shown, these subjects will enter the ferric maltol treatment phase Visit 2.
- 8. Subjects who have at least one dose of study medication and withdraw early from the study undergo Visit 7 (Day 94-98) assessments (excluding those who have withdrawn consent).
- 9. Visit 7 is conducted by telephone, unless the subject has an ongoing AE that requires physical examination or investigations for assessment/management. Visit 7 will take place 10-14 days after Visit 6 (Week 12) unless subject discontinued treatment early. All withdrawn subjects should undergo Visit 7 within 10-14 days after the last dose of study drug (if the subject agrees in the case of withdrawn consent).
- 10. Visit Windows: Maximum of 28 days between screening and pre-assignment phase. The Subject must visit to complete:
 - a. Visit 3: must be 7-10 days from Visit 2
 - b. Visit 4: +/- 5 days relative to date of Visit 2/first dose administered
 - c. Visits 5 to 6: +/- 5 days relative to date of Visit 2/first dose administered

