10.8.2 Pharmacokinetics

Blood samples for maltol and maltol glucuronide on each PK day

Blood samples will be collected at the required times on the PK assessment days relative to the time of ferric maltol morning dosing: pre-dose then two further times between 0.5-10 hours post-dose in the 2-17 years age group and pre-dose then three further times between 1-12 hours post-dose in the 1 m to less than 2 years age group (see Section 10.3 and section 10.4).

Following collection and mixing, blood samples will be centrifuged, and the resultant plasma samples separated and stored at -20°C at the study site, prior to collection and onward shipping to the central laboratory on dry ice for subsequent assay of maltol and maltol glucuronide plasma concentrations using appropriately validated bioanalytical methods. Full

CONFIDENTIAL Page 61 of 80

details of the required sample collection, processing and handling logistics will be specified in the study specific Laboratory Manual. Samples will be destroyed at the end of the study, once all analyses are complete.

Blood samples for iron markers on each PK day

Blood samples will be collected at the required times on the PK assessment days, relative to the time of ferric maltol dosing: pre-dose then two further times between 0.5-6 hours post-dose in the 2-17 yrs age group. Same times as blood samples for maltol/maltol glucuronide for each individual (see Section 10.3 and section 10.4.).

Following collection and mixing, blood samples will be centrifuged, and the resultant serum samples separated and split into 2 aliquots at each timepoint. Ambient serum samples will be shipped to the central laboratory for subsequent assay of serum iron, transferrin, transferrin saturation (TSAT), total and unsaturated iron binding capacity (TIBC, UIBC. Frozen serum aliquot will be stored at site (-20°C) for later onward shipping on dry ice to the central laboratory. Full details of the required sample collection, processing and handling logistics will be specified in the study specific Laboratory Manual. Samples will be destroyed at the end of the study, once all analyses are complete.

PK blood sample scheduling in the 2-17 yrs age groups:

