 - Subjects randomised to ferrous sulfate oral liquid will not need to complete the PK period, they will remain on oral ferrous sulfate liquid until Week 12.
 - Ferrous sulfate 125 mg/ml (25 mg elemental iron) or equivalent dose will be used for all children/adolescents. To maximise the iron replenishment for subjects within this group as well; aged 2 17 yrs will be dosed 0.24ml (6mg elemental iron) per kg body weight per day, up to a maximum of 8ml given daily in two divided doses.
- Assigned treatment phase: 12 weeks open label treatment for ferric maltol children aged
 1 month to less than 2 years.

- Once the PK samples collected from the pre-assignment phase have been analysed for subjects aged 1 month to less than 2 years, and following data review it has been confirmed that they can enroll in the treatment phase, they will be assigned to receive ferric maltol oral suspension and start the 0.1 ml/kg/dose, BID (Maximum 2.5ml BID) dose on Visit 2 and continue for 7-10 days. On Visit 3 (PK Day 2), following baseline pre-dose blood sample and urine sample, subjects will take a single dose of 0.1 ml/kg ferric maltol suspension under supervision. Further three PK blood and urine samples will be collected up to 12 hours post dose. Subjects will continue until week 12.
- End of study: Week 12 visit.
- Post-treatment safety follow-up: 10-14 days following study completion of the treatment period or premature discontinuation.

Table 2.1: Schedule of Assessments for subjects aged 2 years-17 years.

	SCREENING		TREATMENT				FOLLOW- UP
Duration	Up to 21 days	(e	12 quivale	: WEE		ays)	10-14 days
Day		1	7- 10	28	56	84	94-98
Visit 11	1	2	3 8	4	5	6	7 ^{9,10}
Informed Consent	х						
Eligibility ^{1,8}	х	х	х				
Demographics	Х						
Medical History	х						
Physical Examination	х					х	
Vital Signs ²	х	х	х	х	х	х	
Urine Pregnancy Test 4	х	х	х	Х	х	х	
Clinical Laboratory tests ⁵	х					х	
Haematology ⁶	х			Х		х	
Iron markers ⁶	х			Х		х	
PK assessment PK Blood Sampling for maltol/maltol glucuronide and iron markers ⁷		Х	х				
Randomisation ⁸		х					
Dispense Study Drug		х	Х	Х	Х		
Return Study Drug for Accountability			х	х	х	х	

	SCREENING	TREATMENT			FOLLOW- UP			
Duration	Up to 21 days	12 WEEKS (equivalent of 84 days)						
Day		1	1 7- 28 56 84		94-98			
Visit 11	1	2	3	4	5	6	7 ^{9,10}	
Palatability questionnaire		х		х				
Adverse Events		х	х	х	х	х	х	
Concomitant Medications and Procedures	х	х	х	х	х	Х	х	
Compliance reminder		х	х	х	х	х		

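### The infant accumulation safeguard acts only on the single-dose urine day; no review is attached to Visit 3, the first repeat-dose and first plasma maltol reading in infants

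*Protocol*

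**What the plan says.** - **Why infants are handled separately.** Protocol 5.5 gives infants a single dose before any repeat dosing because of the enzyme isoform that glucuronidates maltol.
- **The hold.** Protocol 7.5 begins "If there is any sign of accumulation of maltol or glucuronide in the pre-assignment phase PK day". If it is triggered, recruitment of infants stops, and none enters treatment until the risk has been assessed and a substantial amendment approved.
- **What that day measures.** Protocol 10.4, note 6: one supervised dose of 0.1 ml/kg, one pre-dose urine and three post-dose urines, the last at 7 to 12 hours. No blood is taken.
- **Who acts.** Under 9.2 the Medical Monitor "will make a recommendation to the investigator based on preassignment results", and the investigator decides on entry.
- **What Visit 3 measures.** The infant visit-window note in 10.4 reads "Visit 3: must be 7-10 days from Visit 2". Blood and urine are taken before the morning dose, then three post-dose samples of each. Objective 3 in 6.2 specifies "plasma (PK Day 2 only) and urine concentration of maltol and maltol glucuronide", so Visit 3 is the only plasma maltol reading in infants.
- **What follows Visit 3.** Protocol 7.1: "urine samples will be taken at three timepoints up to 12 hours. Subjects will continue treatment until week 12". SAP 2.2.1: "Further three PK blood and urine samples will be collected up to 12 hours post dose. Subjects will continue until week 12". The synopsis says the same.
- **When plasma is assayed.** Under 10.8.2 plasma is frozen at site "prior to collection and onward shipping to the central laboratory on dry ice for subsequent assay". No turnaround is stated, and sample logistics are left to the Laboratory Manual.
- **General powers.** In 7.5 the investigator may stop a subject whose wellbeing is in jeopardy. In 7.6 the Sponsor may halt a dose group, and 14.7 mentions review of emerging clinical and safety data. No discontinuation reason in 7.5 is a PK result.

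**The concern.** Accumulation is a repeat-dose phenomenon, and a single-dose profile can only predict it. The plan takes the prediction seriously enough to close the cohort until a substantial amendment is approved. It attaches no decision to the direct observation about a week later, when trough urine and plasma are available. At entry the default is not to dose. After entry the default is to keep dosing, whatever the Visit 3 samples might show.

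The infant schedule in 10.4 adds to this. Clinical chemistry is drawn at Screening and Day 84, and haematology and iron markers at Screening, Visit 2 and Day 84. Visit 3 is therefore the only scheduled blood draw between Visit 2 and Day 84. If it is not read in time, no scheduled blood result can inform a stop for that infant, or a pause for infants about to start. Up to 12 infants are affected.

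**Working it through.** The plan gives no figure of its own to reproduce. The check has three parts.

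**1. Which result triggers what**

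| | Pre-assignment day | Visit 3 (PK Day 2) |
|---|---|---|
| Dosing before sampling | None (one dose on the day) | About a week, twice daily |
| Samples per infant | 4 urine | 4 urine and 4 blood |
| Named reviewer | Medical Monitor, investigator (9.2) | None |
| Action on accumulation | Cohort hold (7.5) | None stated |
| Next step in the text | Entry only if the result is satisfactory | Continue to week 12 |

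**2. Timing and doses**

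Inputs are from Protocol 10.4 and 5.5.2. Visit 3 is scheduled on Day 7-10. Its window note allows 7 to 10 days after Visit 2, which is Day 8-11. The full span is therefore Day 7 to Day 11. Visit 4 is Day 28 ± 5, so Day 23 to Day 33. Treatment is 84 days, twice daily.

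- Planned doses: 84 × 2 = 168.
- Doses before Visit 3: (7 − 1) × 2 = 12 to (11 − 1) × 2 = 20.
- Visit 3 to Visit 4: shortest 23 − 11 = 12 days, longest 33 − 7 = 26 days.
- Doses remaining at Visit 4: (84 − 33) × 2 = 102 to (84 − 23) × 2 = 122.
- Visit 3 samples in the cohort: (1 pre-dose + 3 post-dose) × 2 matrices × 12 infants = 96.

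A result returned within 12 days would precede Visit 4 dispensing in every permitted schedule, with well over half of the planned doses still avoidable (102/168 = 61%; 122/168 = 73%).

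**3. How much accumulation is plausible**

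For linear kinetics and 12-hourly dosing, the fraction left at 12 hours is 2^(−12/t½), and the steady-state accumulation ratio is R = 1/(1 − 2^(−12/t½)). The adult half-lives in Protocol 5.4.2 are 0.8 h (maltol) and 1.1 h (glucuronide). The documents give no infant half-life, so 4 to 24 h is an assumed range.

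| Half-life (h) | Left at 12 h | R |
|---|---|---|
| 0.8 (adult) | 0.003% | 1.00 |
| 1.1 (adult) | 0.05% | 1.00 |
| 4 (assumed) | 12.5% | 1.14 |
| 8 (assumed) | 35% | 1.55 |
| 12 (assumed) | 50% | 2.00 |
| 24 (assumed) | 71% | 3.41 |

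If infants clear maltol as adults do, accumulation is negligible. The ratios that would matter go with a large residue at 12 hours, which the pre-assignment urine is designed to reveal.

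**The case against.** The strongest reply is that the entry check already does most of the work. It is made for each infant and covers one full dosing interval. It admits an infant only if maltol is back at baseline or at a level that rules out accumulation. Under linear kinetics a dose cleared within the interval accumulates very little. The documents give some support for linearity, though not in infants: glucuronide exposure was dose-proportional in adults and, with a slight Day 10 Cmax deviation, at 10-17 years. The CKD study saw no clinically significant accumulation. This stands, and it is why the residual risk is low. Its limit is that the entry check has no numeric threshold and uses urine only.

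Second, 7.5, 7.6 and 14.7 let the investigator or Sponsor stop, and adverse events are collected at every infant visit from pre-assignment on. This also stands, but these are permissions. None requires anyone to look at the Visit 3 result before Day 84.

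Third, the missing turnaround is silence rather than a statement that assay will be late. The Laboratory Manual, which is not among the documents, may set one. Even so, a turnaround time would not supply a reviewer, a criterion or an action.

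A reader might infer more than the documents support:

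- *That infants must be dosed despite accumulation.* The continuation sentence is ordinary schedule text, used in 7.1 for ages 2-17 as well, and it remains subject to 7.5 and 7.6.
- *That infant PK goes unanalysed because SAP 3.5.4 derives parameters for 2-17 years only.* Protocol 12.2.2 lists infant urinary excretion and renal clearance for both PK days, and SAP 3.5.3 summarises infant concentrations. These are descriptive outputs with no decision attached, but the data are analysed.
- *That 5.6 or the adult Day 1 and Day 8 sampling establishes a safety stopping rule for PK.* Neither passage describes one.

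**Conclusion.** The point holds as a mismatch of scope in a stated safety rule. The accumulation hold and the Medical Monitor's role end at the single-dose urine day. The first repeat-dose and plasma evidence, obtained after 12 to 20 of 168 doses, prompts no required review, although 102 to 122 doses would remain at Visit 4.

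The dose counts measure the opportunity to act; they do not measure harm. Material accumulation is unlikely in an infant who has passed the 12-hour check, and discretionary stops exist. This is a cheap safety improvement, and the documents do not show that infants are left unprotected.

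The conclusion assumes that no document outside the protocol and SAP, such as the Laboratory Manual, already requires Visit 3 infant results to be reported and reviewed during treatment.

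**What to change.** 1. **Protocol 7.5 and 9.2:** require infants' Visit 3 plasma and urine maltol and maltol glucuronide to be assayed during the study and reported to the Medical Monitor before Visit 4 dispensing. State a turnaround of about 12 days or less, from sampling to report, in 10.8.2.
2. **Criterion:** clinical pharmacology sets it before the first infant reaches Visit 3. The main comparison is the Visit 3 pre-dose (trough) urine against the same infant's 7-12 h urine after the single dose, with plasma alongside. The drug-naive pre-assignment sample should not be used alone, because the previous evening's dose can leave some glucuronide without any accumulation.
3. **Action if the criterion is met:** withhold that infant's dosing and pause new infant starts while the Medical Monitor and Sponsor assess the risk under 7.5 and 7.6. Review other treated infants before their next dispensing. An automatic cohort stop on any sign at all would be too sensitive here.
4. **Synopsis, 7.1 and SAP 2.2.1:** make continuation to week 12 subject to this review, with a cross-reference to 7.5.

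**Cost:** wording changes, a criterion to be agreed, and earlier, unbatched assay of up to 96 samples that are already collected. No extra blood or visits. There is a small chance of a pause on a false alarm.
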